### 3.3 Inclusion of Minority Populations

Women of all ethnic groups are eligible for this phase II trial. This study is designed to include minorities as appropriate. However, the trial is not designed to measure differences in intervention effects. The population of Canada is ethnically diverse and the proportions of different ethnic groups in the community are provided in the table below. Universal access to health care will ensure that there is no discrimination on the basis of race or gender Guide to Canadian Human Rights Act: [www.chrc-ccdp.ca/public/guidechra.pdf](http://www.chrc-ccdp.ca/public/guidechra.pdf).

Individual hospital registries and databases do not routinely collect racial data, under the direction of the Canadian Human Rights Code.

The population demographics and distribution of minorities in various regions of Canada is included in the table 1 below:

**Table 2: Visible minority population by Consortium Provinces (2001 Census)**

	British Columbia	Alberta	Ontario	Nova Scotia	Total
Total population of province	3,868,870	2,941,150	11,285,550	897,570	18,993,140
Visible Minorities	Population	Population	Population	Population	Population
Black	25,465	1%	31,390	1%	411,095 4%
			20		19,670 2% 487,620 3%
Asian	768,435	%	268,660	9%	1,513,825 13% 12,630 1% 0 %
Latin American (Hispanic)	23,880	1%	18,745	1%	106,835 1% 520 0% 149,980 1%
Visible minority, not included elsewhere	4,195	0%	4,220	0%	78,915 1% 1,170 0% 88,500 0%
Multiple visible minority	14,465	0%	6,910	0%	42,375 0% 535 0% 64,285 0%
Total Visible minority population	836,440	%	329,925	%	2,153,045 19% 34,525 4% 6 %

Source: Statistics Canada, Census of Population.

We have compiled some data from our consortium of representation of minorities on previous clinical trials, and the distribution is as follows:

**Table 3: Population Percentage of Minority and Gender of entering PMHC Trials**

	2002	2003	2004
Visible Minorities			
Black	3.6	0	2.8
Asian	7.2	9.0	8.4

Hispanic	2.4	3.0	1.7
Total	13.2	12	12.9
Women	44.6	49.3	46.9

## 4. REGISTRATION PROCEDURES

### 4.1 General Guidelines

Following registration, patients should begin protocol treatment within 72 hours. Issues that would cause treatment delays should be discussed with the Principal Investigator. If a patient does not receive protocol therapy following registration, the patient's registration on the study may be canceled. The Central Office Study Coordinator should be notified of cancellations as soon as possible.

Each participating institution will order DCTD-supplied agents directly from the Pharmaceutical Management Branch (PMB) of CTEP. Agents may be ordered by a participating site only after the initial IRB approval for the site has been forwarded by the Coordinating Center to the CTEP PIO ([[contact]](mailto:[contact])) except for Group studies. In the event of any problems or issues with product supply, PMB must be contacted directly.

### 4.2 Registration Process

- Prior to registering a patient, each institution must have submitted all necessary regulatory documentation to the PMH Phase II Consortium Central Office. CRFs will only be sent once this has been received.
- No patient can receive protocol treatment until registration with the Central Office has taken place. All eligibility criteria must be met at the time of registration. There will be no exceptions. Any questions should be addressed with the Central Office prior to registration.
- The eligibility checklist must be completed, and signed by the investigator prior to registration.
- Sites will fax in the signed, completed eligibility checklist to the central office at [contact]. The central office will then review the checklist and once eligibility has been confirmed fax back a confirmation sheet indicating the unique study number for the subject and confirmation of entry into the trial. Only after this faxed confirmation sheet has been received back from central office, can the patient receive the study drug.

- To ensure immediate attention is given to the faxed checklist, each site is advised to also call the study coordinator listed on the front sheet or call the central office at [contact] [name] or page the program manager at [contact]. Patient registration will be accepted between the hours of 9 am to 5 pm Monday to Friday, excluding Canadian statutory holidays when the central office will be closed.

especially (1) patients with comorbidities associated with adrenal dysfunction, (2) patients with pre-existing adrenal insufficiency (primary or secondary), and (3) patients with concomitant stress (*e.g.*, fever, infection, bleeding, serious accident, surgery) that may precipitate overt adrenal insufficiency in the presence of subclinical sunitinib-induced adrenal toxicity. If clinically indicated, objective testing for adrenal gland function should be conducted.

- Patients with bulky solid tumors should be monitored closely for pneumothorax, intestinal fistulae, or intestinal perforation in the event of rapid tumor destruction.
- Patients should be alerted to the possibility that sunitinib capsules can cause a yellow discoloration of the skin on direct contact. If this happens, the patient should wash immediately with soap and water.

## 5.2 General Concomitant Medication and Supportive Care Guidelines

The case report form (CRF) must capture the concurrent use of all other drugs, over-the-counter medications, or alternative therapies including herbal supplements, specifically, St. John's wort. The Principal Investigator should be alerted if the patient is taking any agent known to affect or with the potential to affect selected P450 isoenzymes. (A comprehensive list of CYP3A4-interactive agents is provided in Appendix C.)

### 5.2.1 Concomitant Medications

- Use of agents with **proarrhythmic potential** (terfenadine, quinidine, procainamide, disopyramide, sotalol, probucol, bepridil, haloperidol, risperidone, indapamide, and flecainide) is not permitted during the study. A comprehensive list of agents with proarrhythmic potential can be found at <http://torsades.org>. Refer to Appendix J.
- Sunitinib is primarily metabolized by liver enzymes, particularly **CYP3A4**. Co-administration of potent inhibitors or inducers of this enzyme can result in significant changes in exposure to sunitinib (*e.g.*, a mean 1.8-fold increased exposure with ketoconazole and a mean 4-fold decrease with rifampin). For this reason, use of the following agents is not permitted before or during the study:

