- Pre-existing adrenal insufficiency (primary or secondary)

3.2.10 Because sunitinib is metabolized primarily by the CYP3A4 liver enzyme, the eligibility of patients taking medications that are potent inducers or inhibitors of that enzyme will be determined following a review of their case by the Principal Investigator. (A list of potent CYP3A4 inducers or inhibitors can be found in Section 5.2.) Every effort should be made to switch patients taking such agents or substances to other medications, particularly patients who are taking enzyme-inducing anticonvulsant agents. A comprehensive list of medications and substances known or with the potential to alter the pharmacokinetics of sunitinib through CYP3A4 is provided in Appendix C.

3.2.11 Patients with a pre-existing thyroid abnormality who are unable to maintain thyroid function in the normal range with medication are ineligible.

3.2.12 Patients with known brain metastases should be excluded because of their poor prognosis and because they often develop progressive neurologic dysfunction that would confound the evaluation of neurologic and other adverse events.

3.2.13 Patients with uncontrolled intercurrent illness including, but not limited to, ongoing or active infections or psychiatric illness/social situations that would limit compliance with study requirements are ineligible.

3.2.14 Pregnant women are excluded from this study because sunitinib is an antiangiogenic agent with the potential for teratogenic or abortifacient effects. Because there is an unknown but potential risk for adverse events in nursing infants secondary to treatment of the mother with sunitinib, breastfeeding should be discontinued if the mother is treated with sunitinib malate.

3.2.15 HIV-positive patients on combination antiretroviral therapy are ineligible because of the potential for pharmacokinetic interactions with sunitinib. In addition, these patients are at increased risk of lethal infections when treated with marrow-suppressive therapy. Appropriate studies will be undertaken in patients receiving combination antiretroviral therapy when indicated.

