#### **Inhibitors – prohibited 7 days before dosing and during study.**

azole antifungals (ketoconazole, itraconazole)	verapamil
clarithromycin	HIV protease inhibitors (indinavir, saquinavir, ritonavir, atazanavir, nelfinavir)
erythromycin	delavirdine
diltiazem	

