#### **Inducers – prohibited 12 days before dosing and during study.**

rifampin	phenytoin
----------	-----------

rifabutin	St. John's wort
carbamazepine	efavirenz
phenobarbital	tipranavir

A comprehensive list of CYP3A4 inhibitors, inducers, and substrates is provided in Appendix C.

- **Steroid use** is not recommended during sunitinib treatment unless absolutely necessary (*e.g.*, for treatment of adverse events or protocol-required premedication) because many steroids (*e.g.*, prednisone, prednisolone, dexamethasone, etc.) effectively lower sunitinib exposure through CYP3A4 interactions.
- The use of coumarin-derivative **anticoagulants** such as warfarin (Coumadin®) is not recommended, although doses of up to 2 mg daily are permitted for prophylaxis of thrombosis.

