**Solubility in various solvents:**

Solvent	Solubility (mg/mL)
Tetrahydrofuran	0.2
1-Butano:Water (80/20 v:v)	1.0
N, N-Dimethylacetamide	3.0

**Mode of Action:** Sunitinib malate is a receptor tyrosine kinase inhibitor involved in tumor proliferation and angiogenesis, specifically inhibiting platelet derived growth factor receptor, vascular endothelial growth factor receptor, stem cell factor receptor, Fms-like tyrosine kinase-3 receptor, and *ret* proto-oncogene.

**How Supplied:** Sunitinib malate is supplied by Pfizer and distributed by DCTD/NCI as 12.5 mg, 25 mg, and 50 mg capsules with mannitol, croscarmellose sodium, povidone, and magnesium stearate. Each opaque plastic bottle contains 30 capsules.

Capsule strength	Description
12.5 mg	Swedish Orange, Size 4 hard gelatin capsule
25 mg	Swedish Orange/Caramel, Size 3 hard gelatin capsule.
50 mg	Caramel, Size 2 hard gelatin capsule

**Storage:** Store at controlled room temperature (15 to 30^0 C), and protect from light.

**Stability:** Shelf-life studies for sunitinib capsules are ongoing.

**Route of Administration:** Oral. Sunitinib malate may be administered without regard to meals.

**Potential Drug Interaction:** Sunitinib malate is metabolized primarily by liver enzymes, particularly CYP3A4. CYP3A4 inducers (e.g., rifampin,

dexamethasone) and CYP3A4 inhibitors (e.g., grapefruit juice, ketoconazole) should be avoided, if possible. Rifampin lowers sunitinib malate Cmax concentration by more than 2-fold. Ketoconazole increases sunitinib malate Cmax by 1.6 fold. Dose reduction with the CYP3A4 inhibitors is recommended, based on clinical symptoms.

Concomitant treatment with dysrhythmic drugs, *i.e.*, terfenadine, quinidine, procainamide, sotalol, probucol, bepridil, haloperidol, risperidone, and indapamide, is not recommended.

**Patient Care Implications:** A yellow discoloration of the skin area may result following direct contact with the capsules. Wash the exposed area with soap and water immediately.

**Availability:** Sunitinib malate is an investigational agent supplied to investigators by the Division of Cancer Treatment and Diagnosis (DCTD), NCI. Sunitinib malate is provided to the NCI under a Collaborative Agreement between Pfizer and the DCTD, NCI (see Section 11.3).

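### Sections 3.2.10, 5.2.1 and 8 give three incompatible rules for the same named potent CYP3A4 inhibitors and inducers, so enrolment and sunitinib exposure depend on the section a site follows

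*Combined protocol and SAP*

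**What the plan says.** Three sections deal with patients who take potent CYP3A4 inhibitors or inducers.

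- **Section 5.2.1 (treatment plan).** "use of the following agents is not permitted before or during the study". Two lists follow. Inhibitors, including ketoconazole, are "prohibited 7 days before dosing and during study". Inducers, including rifampin, phenytoin, carbamazepine and phenobarbital, are "prohibited 12 days before dosing and during study". No exception is given. The reason stated is a mean 1.8-fold rise in sunitinib exposure with ketoconazole and a mean 4-fold fall with rifampin.
- **Section 3.2.10 (exclusion criteria).** The decision is left to the Principal Investigator: "the eligibility of patients taking medications that are potent inducers or inhibitors of that enzyme will be determined following a review of their case". The drugs meant are those in the treatment plan: "A list of potent CYP3A4 inducers or inhibitors can be found in Section 5.2". On changing the co-medication it says: "Every effort should be made to switch patients taking such agents or substances to other medications".
- **Section 8 (pharmaceutical information, drug interactions).** CYP3A4 inducers, with rifampin and dexamethasone as examples, and inhibitors, with grapefruit juice and ketoconazole as examples, are to be avoided where possible. It adds: "Dose reduction with the CYP3A4 inhibitors is recommended, based on clinical symptoms".

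Section 5.1 starts every patient at 50 mg. Section 6 holds the dose levels and the dose-modification rules and has no entry for an interacting co-medication. Section 4.2 allows no exceptions to the eligibility criteria at registration.

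**The concern.** The three sections do not merely differ in detail. One forbids the drugs, one admits the possibility of enrolling a patient who takes them, and one tolerates them and describes how to adjust sunitinib while they are taken. Two sites following the same protocol could treat the same candidate differently, and each could cite a section in support.

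At stake are safety and the interpretation of the trial. The protocol itself treats these interactions as large enough to justify a ban. A patient kept on an inducer would receive much less sunitinib than intended, and one kept on an inhibitor more. Under Section 12.4.2, eligible patients remain in the main response analysis and an incorrect administration does not remove them. With decisions taken at 1 response in 15 and 4 in 30, the rule on who enters, and at what exposure, should have one meaning.

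**Working it through.** **Step 1. Do the three sections concern the same drugs?** Section 3.2.10 refers explicitly to the Section 5.2 list, so its scope is the list that 5.2.1 bars. Section 8 speaks of CYP3A4 inhibitors and inducers in general, but two of its four examples, ketoconazole and rifampin, are on the 5.2.1 lists by name. The other two, grapefruit juice and dexamethasone, are not. The overlap is therefore complete for 3.2.10 and certain for at least two named drugs in Section 8.

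**Step 2. What does each section imply for a patient on a listed drug?**

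| Question | 5.2.1 | 3.2.10 | 8 |
|---|---|---|---|
| May the patient be dosed while taking it? | No | Open, after case review | Yes, if it cannot be avoided |
| Is a switch required? | In effect, yes | Best effort only | Not stated |
| Washout before dosing | 7 days (inhibitor), 12 days (inducer) | Not cited | Not stated |
| Sunitinib dose change | None, as use is barred | None stated | Symptom-based reduction, inhibitors only |

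The first row cannot be satisfied by all three at once. A reduction of sunitinib because of an inhibitor presupposes that the inhibitor continues, which 5.2.1 rules out for the listed inhibitors.

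**Step 3. Does any section set precedence?** No. The opening of Section 5.2 asks that the Principal Investigator be alerted to any agent affecting P450 enzymes, without saying that a listed agent is barred. Section 6 does not mention co-medication as a ground for changing the sunitinib dose.

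**Step 4. How large is the exposure effect, by the protocol's own means (Section 5.2.1)?**

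- Ketoconazole: exposure × 1.8.
- Rifampin: exposure × 1/4 = 0.25.
- Ratio of the two: 1.8 / 0.25 = 7.2.

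The 7.2 compares a patient kept on one drug with a different patient kept on the other. It is not a spread that the three rules create for one patient; that patient's contrast is 1.8-fold or 4-fold against no interaction.

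**Step 5. Is any design figure affected?** The rule in Section 12.1 is to stop at 0 of 15 and otherwise continue to 30, with success at 4 or more. With X1 and X2 the responses among the first and second 15, each binomial(15, p):

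- P(stop) = (1 − p)^15. At p = 0.05 this is 0.463 (stated: about 0.46).
- Expected N = 15 + 15 × (1 − 0.463) = 23.05 (stated: 23.05).
- P(success) = sum over x ≥ 1 of P(X1 = x) × P(X2 ≥ 4 − x). This gives 0.058 at p = 0.05 and 0.865 at p = 0.20 (stated: 0.058 and 86.5%).

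All stated figures reproduce.

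**Step 6. Sensitivity only.** Suppose a fraction f of patients stays on an inducer and responds at 5% instead of 20%. Both values are assumptions; the documents give neither. Then p = 0.20 − 0.15f.

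- f = 1/30: p = 0.195, power 0.851.
- f = 0.10: p = 0.185, power 0.818.
- f = 0.20: p = 0.17, power 0.760.

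**The case against.** The best defence is that the sections have different jobs. Section 3.2.10 is a screening step: the case is reviewed and a switch is attempted. Section 5.2.1 then binds anyone who is dosed, so a patient who passes review must still meet the 7- or 12-day window. On this view only Section 8 is out of line, and it is general drug information with a wider scope. For agents outside the 5.2.1 lists its softer wording contradicts nothing; 5.2.1 itself allows steroids when unavoidable. Patients on combination antiretroviral therapy are excluded separately by 3.2.15, which narrows the overlap further.

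Much of this is fair. The screening reading is workable, but a reader has to supply it: 3.2.10 does not make the switch a condition, does not cite the windows, and speaks of eligibility for patients taking the drugs. Nor does that reading rescue Section 8 for ketoconazole and rifampin, which it names and 5.2.1 bars.

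Three stronger inferences may tempt a reader, and the documents do not support them.

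- **That Section 8 enrols patients at a lower starting dose.** Its reduction responds to symptoms and covers inhibitors only. Nothing in it alters the 50 mg start in 5.1, and it changes no dose for inducers. Some symptoms would also meet a Section 6 criterion in their own right.
- **That 50 mg behaves like 90 mg (50 × 1.8) or 12.5 mg (50 / 4).** The second lies outside the 25–100 mg multiple-dose range for which Section 2.2 reports proportionality. The first counts parent drug only: Section 2.2 reports a small decrease in the metabolite SU12662 with ketoconazole and calls that metabolite comparably active. The rifampin data come from healthy male volunteers.
- **That the trial loses its power.** Nothing in the documents supports 10% or 20% of patients remaining on an inducer. One such patient in 30 leaves 0.851, and even the 10% case stays above the 0.80 implied by the target β of about 0.20.

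**Conclusion.** The contradiction stands. For the same named agents, Section 5.2.1 prohibits, Section 3.2.10 leaves to case review, and Section 8 tolerates with a symptom-based dose reduction for inhibitors. Whether a patient on a listed agent is enrolled, and at what exposure, depends on the section followed. For inhibitors, later sunitinib dosing may depend on it too.

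The size is best expressed by the protocol's own mean factors, 1.8-fold up and 4-fold down; these are averages for one inhibitor and one inducer and need not hold for every listed drug. How many patients would be affected cannot be judged from the documents. The finding rests on comparing the texts and on no assumption about prevalence. It is an inconsistency between operative rules, not an error in the sample size, error rates or power. It deserves correction because it bears on safety and exposure and is cheap to remove.

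**What to change.** - Reconcile Sections 3.2.10, 5.2.1 and 8 into one rule for the listed agents. State whether they are barred or reviewable, both for eligibility and on study, and whether the 7- and 12-day windows apply to every patient. Remove the superseded wording.
- State separately how agents outside the 5.2.1 lists are handled, such as grapefruit juice and dexamethasone.
- If a sunitinib dose change for co-medication is kept, cross-reference it in Section 6. If it is not kept, remove the sentence from Section 8.

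Which rule applies is a clinical decision for the sponsor, and this review does not propose one. The cost is a wording amendment with no added patients or procedures. If the stricter text is kept, a few candidates may need a switch of medication or become ineligible.

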#### **Inhibitors – prohibited 7 days before dosing and during study.**

azole antifungals (ketoconazole, itraconazole)	verapamil
clarithromycin	HIV protease inhibitors (indinavir, saquinavir, ritonavir, atazanavir, nelfinavir)
erythromycin	delavirdine
diltiazem	

#### **Inducers – prohibited 12 days before dosing and during study.**

rifampin	phenytoin
----------	-----------

rifabutin	St. John's wort
carbamazepine	efavirenz
phenobarbital	tipranavir

A comprehensive list of CYP3A4 inhibitors, inducers, and substrates is provided in Appendix C.

- **Steroid use** is not recommended during sunitinib treatment unless absolutely necessary (*e.g.*, for treatment of adverse events or protocol-required premedication) because many steroids (*e.g.*, prednisone, prednisolone, dexamethasone, etc.) effectively lower sunitinib exposure through CYP3A4 interactions.
- The use of coumarin-derivative **anticoagulants** such as warfarin (Coumadin®) is not recommended, although doses of up to 2 mg daily are permitted for prophylaxis of thrombosis.

#### 5.2.2 Supportive Care

- **Nausea/vomiting:** Patients with treatment-related nausea should be treated initially with a phenothiazine (prochlorperazine – 10 mg every 8 hours orally as needed, or promethazine – 12.5-25 mg IV every 6 hours as needed). If this is inadequate, a benzodiazepine should be added until acute nausea is controlled or toxicity is limiting. Should this prove inadequate acutely, a steroid may be added (*e.g.*, dexamethasone 4 mg every 6 hours as needed).
- After acute nausea has resolved, consideration should be given to initiation of prophylactic antiemetic therapy. If nausea recurs despite reasonable medical intervention (as outlined above), dose reduction will be needed as described in Section 6.
- **Diarrhea** should be managed with loperamide: 4 mg at first onset, then 2 mg every 2-4 hours until diarrhea is controlled (maximum = 16 mg loperamide per day).
- **Hand-foot syndrome** may be treated with topical emollients (such as Aquaphor), topical/systemic steroids, and/or antihistamine agents. Vitamin B6 (pyridoxine; 50-150 mg orally each day) may also be used.
- Patients with **neutropenic fever** or infection should be evaluated promptly and treated with IV antibiotic therapy or therapeutic colony-stimulating factors as appropriate following the ASCO guidelines [*J Clin Oncol* 18(20):3558-85, 2000].. Packed red blood cell and platelet transfusion should be administered as clinically indicated. Erythropoietic agents may be used at the discretion of the treating physician.

